Number of subjects needed	72 patients
Planned study period	
Expected start date of inclusion: November 2012
 
Expected completion date of inclusion: April 2016
 
Primary endpoint analysis: April 2018
 
End of study: January 2019

EXAMINATION AND FOLLOW-UP SCHEDULE

	BEFORE TREATMENT	DURING EMBOLIZATION OR CHEMOEMBOLIZATION		DURING TREATMENT WITH EVEROLIMUS (24 months maximum)	AFTER STOPPING TREATMENT WITH EVEROLIMUS (after 24 months)
	Within 4 weeks prior to inclusion	Within 7 days prior to each embolization or chemoembolization	After embolization or chemoembolization	Every 3 months +/- 1 week	Every 3 months +/- 1 week
Informed consent	X				
CLINICAL EXAMINATION					
Weight, general condition WHO	X	X		X	X
Functional symptoms related to hormonal hypersecretion	X				
Medical and surgical history and treatments related to the endocrine tumor	X				
MORPHOLOGICAL EXAMINATION					
Triphasic thoracoabdomino-pelvic CT (to be performed in the investigating center, without injection, arterial time, portal time) *with measurement of liver metastases according to RECIST v1.1 criteria	X*		X**	X*	X***
ECG ± cardiological opinion if necessary	X				
BIOLOGICAL ASSESSMENT					
CBC/platelets, total and conjugated bilirubin, AST, ALT, PAL, creatinine, 24-hour proteinuria if treated with streptozotocin	X	X		X	
INR, TCA	X	X		X	
albumin, urea, blood ionogram, GGT	X			X	
Serum cholesterol and triglycerides, fasting blood glucose and HbA1c	X			X	
Chromogranin A, urinary 5HIAA	X			X	
B viral serology (HBV-DNA, HBsAg, anti-HBsAb, anti-HBcAb) and C****	X			****	
Pregnancy test for women of childbearing age	X (within 7 days of starting treatment)				

*With target measurement according to RECIST v1.1 criteria

**To be performed for technical reasons only. Measurements should not be used for evaluation of tumor response

*** If everolimus is discontinued for reasons other than hepatic progression, continue morphological monitoring until hepatic progression occurs

**** In case of B and C viral serology, follow up the DNA and RNA load respectively every 3 to 6 weeks (see table 2-2 and 2-3)

I. OBJECTIVES OF THE TRIAL

1. Main objective

The primary objective of the study is to determine whether treatment with everolimus for 24 months prolongs progression-free survival according to RECIST 1.1 criteria. The primary endpoint will be progression-free survival at 24 months in patients receiving hepatic embolization or chemoembolization followed by everolimus therapy.

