syndrome, somatostatin analogue therapy is not permitted after embolization or chemoembolization.

VII. EXPECTED TOXICITIES AND DOSE ADJUSTMENT

1. Dose adjustment after the first embolization or chemoembolization

No dose adjustment of doxorubicin or streptozotocin is planned for chemoembolization sessions. There are no plans to adjust the dose of lipiodol for embolization sessions.

Embolization or chemoembolization will only be performed if hematological, renal and hepatic functions are satisfactory i.e. if:

- PNN $\geq 1.5 \times 10^9$ /L,
- Platelets $\geq 75 \times 10^9$ /L
- Hemoglobin ≥ 10 g/dL
- INR $< 1.3N$ or < 3 on anticoagulants or PT ≥ 50
- Creatinine level $\leq 1.5N$
- Total bilirubin $< 1.5N$
- ASAT, ALAT $\leq 5N$
- PAL $< 5N$

In case of grade 3 or 4 non-hematological toxicity attributable to the first embolization or chemoembolization session, no further embolization or chemoembolization is performed. Only everolimus will be continued for a maximum of 24 months.

2. Everolimus dose adjustment

All toxicity will be assessed according to the NCI-CT v4.0 scale (Appendix 4).

The rules for everolimus dose adjustment in case of observed hematological and non-hematological toxicities are defined in Tables 1.1, 1.2.

All interruptions or changes to the study drug must be recorded

Monitoring of suspected everolimus toxicity

Patients whose treatment is temporarily or permanently discontinued due to an adverse event or laboratory abnormality suspected to be related to everolimus should be monitored at least weekly until the adverse event resolves or returns to grade 1. If the patient's treatment is to be delayed for more than 21 days from the day of the next scheduled dose, the patient should be excluded from the study.

Table 1.0 Guidelines for Everolimus Dose Level Changes

Dose level	Dose and frequency of administration
0 (initial dose)	10 mg per day
-1	5 mg per day
-2	5 mg every 2 days

a. **Dose adjustment for non-hematologic and hematologic toxicities**

Table 1-1 Dose adjustment criteria for everolimus toxicity and reinstatement of everolimus therapy

NON-HEMATOLOGICAL AND NON-HEPATIC Toxicity (NCI-CTC V4.0)	Actions

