Grade 2 (except pneumonia - see Table 1-4)	If toxicity is tolerable to the patient, maintain the same dose. In case of intolerable toxicity for the patient, discontinue everolimus until recovery to grade ≤ 1 . Then reintroduce everolimus at the same dose. If an event returns to grade 2, discontinue everolimus until recovery to grade ≤ 1 . Then reintroduce everolimus at the lower dose level.
Grade 3 (except hyperlipidemia*) (except pneumonia - see Table 1-4)	Interrupt everolimus until recovery to grade ≤ 1 . Then reintroduce everolimus at the lower dose level. For pneumonia, consider short-term steroid therapy.
Grade 4	Stopping everolimus
Any non-hematologic toxicity requiring interruption for a period ≥ 3 weeks	Stopping everolimus

*Grade 3 hyperlipidemia (hypercholesterolemia and/or hypertriglyceridemia) should be managed with medical treatments.

Table 1-2

HEMATOLOGICAL Toxicity (NCI-CTC V4.0)	Grade	Actions
Thrombocytopenia	Grade 2 (platelets $< 75, \geq 50 \times 10^9 /l$)	Interrupt everolimus until recovery to grade ≤ 1 ($\geq 75 \times 10^9 /l$). Then reintroduce everolimus at the initial dose. If thrombocytopenia returns to grade 2, discontinue everolimus until recovery to grade ≤ 1 . Then reintroduce everolimus at the lower dose level.
	Grade 3 (platelets $< 50, \geq 25 \times 10^9 /l$)	Interrupt everolimus until recovery to grade ≤ 1 (platelets $\geq 75 \times 10^9 /l$). Then resume everolimus at a lower dose level.

		If thrombocytopenia recurs at grade 2, discontinue everolimus.
	Grade 4 (platelets < 25×10^9 /L)	Stopping everolimus
Neutropenia	Grade 3 (neutrophils < 1, $\geq 0.5 \times 10^9$ /L)	Interrupt everolimus until recovery to grade ≤ 1 (neutrophils $\geq 1.5 \times 10^9$ /L). Then resume everolimus at the initial dose. If PNN returns to grade 3, withhold everolimus until PNN is $\geq 1.5 \times 10^9$ /L. Then resume everolimus at the lower dose level. Discontinue study treatment if a third episode of Grade 3 neutropenia occurs
	Grade 4 (neutrophils < 0.5×10^9 /L)	Interrupt everolimus until recovery to grade ≤ 1 (neutrophils $\geq 1.5 \times 10^9$ /L). Then resume everolimus at the lower dose level. If Grade 3 or 4 neutropenia occurs despite this dose reduction, discontinue everolimus

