* All hepatitis B reactivations should be recorded as a Grade 3 adverse event (CTCAE v 4.0 Other Adverse Events Associated with Metabolic or Biological Abnormalities: Viral Reactivation), unless the investigator considers them life-threatening in which case they should be recorded as a Grade 4 adverse event (CTCAE v 4.0 Other Adverse Events Associated with Metabolic or Biological Abnormalities: Viral Reactivation). The date of viral reactivation is the date on which **both** the DNA and ALAT criteria are met (e.g., for a patient with HBV DNA positive on 01-01-10 and an ALAT level $\geq 5 \times$ ULN on 01-04-10, the date of viral reactivation is 01-04-10).

• Hepatitis C Outbreak Surveillance

The following two categories of patients should be monitored every 6 weeks for HCV reactivation:

- Patients with detectable HCV RNA by PCR analysis in basal state.
- Patients with a known history of hepatitis C virus (HCV) infection, despite a negative baseline viral load test (including those who have been treated and considered "cured")

For the definition of hepatitis C reactivation and guidelines for its management, see Table 2-3 Guidelines for the Management of Hepatitis C.

Table 2-3: Guidelines for the Management of Hepatitis C

HCV outbreak	
For patients with baseline results: detectable HCV RNA, an HCV outbreak is defined as follows:	Discontinue study drug but continue monitoring as part of the study.

Increase in HCV RNA by $2 \log_{10}$ IU/ml AND ALT elevation: $5 \times$ ULN or $3 \times$ baseline, whichever is higher
	

For patients with baseline results: Known history of hepatitis C without detectable HCV RNA, an HCV outbreak is defined as: New appearance of detectable HCV RNA AND ALT elevation: $5 \times$ ULN or $3 \times$ baseline, whichever is higher
	
Discontinue study drug but continue monitoring as part of the study. .

* All hepatitis C outbreaks should be recorded as a Grade 3 event (CTCAE v 4.0 Other Adverse Events Associated with Metabolic or Biological Abnormalities: Viral Outbreak), unless the investigator considers them life-threatening, in which case they should be recorded as a Grade 4 event (CTCAE v 4.0 Other Adverse Events Associated with Metabolic or Biological Abnormalities: Viral Outbreak)

VIII. PATIENT MONITORING DURING TREATMENT AND AFTER WITHDRAWAL OF TREATMENT

1. Monitoring during treatment

Within 7 days prior to each embolization or chemoembolization session

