- Clinical assessment: weight, general condition (WHO)
- Evaluation of the tolerance of the previous embolization or chemoembolization
- Biological check-up:
 - CBC-platelets
 - INR, aPTT, creatinine, bilirubin (total, conjugated), AST, ALT, PAL

NB: An abdominal CT scan may be performed if necessary for technical reasons before the 2nd embolization or chemoembolization session. Caution: this imaging should not be used to evaluate the response to treatment of metastases.

Every 3 months (+/- 1 week) from the date of the first embolization or chemoembolization (except DNA and ARC monitoring for positive serology)

- Clinical assessment: WHO, weight, evaluation of side effects
- Bioassay:
 - CBC/platelets, urea and creatinine + calculated creatinine clearance (Cockcroft formula), blood ionogram
 - INR, aPTT, albumin, alkaline phosphatase, AST, ALT, bilirubin (total and conjugated), gamma-GT
 - Serum cholesterol and triglycerides
 - Fasting blood glucose and HbA1c
 - Chromogranin A, urinary 5HIAA
- If HBV positive, monitor DNA approximately every 3 weeks or 6 weeks depending on the result (see Table 2-2)

- If HCV positive, monitor RNA every 6 weeks (see Table 2.3)
- Morphological assessment: triphasic thoracic-abdominal-pelvic CT scan with target measurement according to RECIST V1.1 criteria (Appendix 3). Evaluation CT scans should be performed in the same center as the initial examination

NOTE: Patients whose treatment is temporarily or permanently discontinued due to an adverse event or laboratory abnormality suspected to be related to everolimus should be monitored at least weekly until the adverse event resolves or returns to Grade 1

2. Post-treatment monitoring protocol

- **After discontinuation of treatment for hepatic progression**
 - After hepatic progression, the clinical, biological and morphological monitoring of the patient will be left to the investigator's discretion
- **After discontinuation of treatment for a reason other than hepatic progression**
(e.g. toxicity, extra-hepatic progression, patient's wish, :)
 - Morphological surveillance: CT every 3 months until liver progression occurs, according to the same modalities as the initial morphological evaluation (triphasic thoraco-abdomino-pelvic CT with target measurement according to RECIST V1.1 annex 3)

IX. STOP PROCESSING THE STUDY

The processing of the study will be stopped in case of:

- Investigator's decision

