Pregnancy is an exclusion criterion in this trial. However, if a pregnancy is discovered after inclusion, the patient must be excluded from the trial. The sponsor should be informed without delay via the serious adverse event reporting form (no severity criteria should be checked). The patient should be followed until the outcome of the pregnancy and this outcome, whatever it may be, should be reported to the sponsor.

Hospitalizations included in the protocol will not be considered an SAE.

c. Undesirable Effect

Any noxious and undesired response to an investigational drug at any dose or to any investigational component. The adverse reaction is serious if it meets the severity criteria (see above).

d. Unexpected Serious Adverse Effect

An unexpected serious adverse reaction is an event that is not mentioned, or that differs in nature, intensity, or evolution from the product's reference document (Investigator's Brochure or RCPs).

In this essay the reference documents will be:

- For everolimus, the Summary of Product Characteristics for Afinitor® (Appendix 6)

The versions of the Investigator's Brochure and PCR (used for the definition of expected or unexpected everolimus) will be the latest available on the anniversary date of the start of the trial.

What to do

The investigator informs the sponsor of all Serious Adverse Events (Expected and Unexpected), whether or not attributable to the research, that occur during treatment and within 30 days of the last treatment administration.

All Delayed Serious Adverse Events (occurring after this 30-day period) considered reasonably related to the protocol treatment(s) or research should be reported without time limitation.

The report is made by faxing the "notification of a serious adverse event" form (Appendix 7), documented as precisely as possible, dated and signed, within 24 working hours of their discovery to the **FFCD's Randomization Management Analysis Center (CRGA): by fax to [name]**

Modalities and duration of follow-up of individuals following the occurrence of adverse events

The investigator is responsible for appropriate medical follow-up of patients until resolution or stabilization of the effect or until the patient's death. This may sometimes mean that this follow-up extends beyond the patient's discharge from the trial.

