Overall survival will be defined as the time interval between the date of inclusion and the date of death regardless of the cause of death or the date of last news for living patients.

Tolerance to treatment will be assessed by:

- duration of treatment, doses received, dose reductions and deferrals
- Toxicities collected at each monthly visit, and described according to NCI-CTC version 4.0 criteria; Grade 3, Grade 4 and Grade 5 toxicities will be reviewed.
- the number and description of SAEs
- the evolution of the WHO performance index.

Calculation of the number of subjects needed

According to the literature, the median progression-free survival after embolization or chemoembolization ranges from 15 to 19 months with a progression-free survival rate of approximately 35%. As there is no information on progression-free survival in the literature, the hypotheses were built on the progression-free survival data.

The assumptions used to calculate the number of subjects are as follows:

H0: a 24-month progression-free survival rate of less than 35% is not acceptable

H1: A 24-month liver progression-free survival rate greater than 35% would demonstrate the utility of everolimus therapy with an expected 24-month liver progression-free survival rate of 50%,

To obtain a power of 80% with a first-species risk of 5% (one-sided), it is required to include 68 patients according to the assumptions established above (using the exact binomial distribution).

Taking into account a rate of lost to follow-up or patients not evaluable for any reason except death, 72 patients will be included.

3. Statistical analysis plan

Populations of analysis

Patients included in the study will be described (ITT) as well as patients not evaluable for the primary endpoint.

A patient is considered evaluable if he or she has received at least one dose of everolimus and one evaluation.

All efficacy analyses will be performed on a modified intention-to-treat basis (evaluable patients) included in the study regardless of eligibility criteria and treatment received.

Tolerability population: the ITT population that received at least one dose of the treatments.

In all cases of discontinuation, the patient remains in the intention-to-treat analysis. There is no exclusion period for a subsequent therapeutic trial.

Main analyses

A statistical analysis plan will be written prior to freezing the database.

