6.1.2 Population of analysis for primary endpoint (PC)

The analysis population for the primary endpoint is defined as the ITT population of evaluable patients. A patient is considered evaluable if he or she has received at least one dose of everolimus and at least one treatment-related imaging.

A patient who dies (from any cause after treatment) or progresses in liver function before 24 months is evaluable and considered a failure for the primary endpoint.

Patients without a 24-month evaluation will be reviewed according to the following rules:

- If the patient has a later assessment (27 months or more) and is not progressing at that time, then they will be considered progression-free at 24 months
- The other patients will be reviewed at a medical review to decide, in view of the patient's entire file, whether they can be considered as failed or as truly non-evaluable (a rate of 5% of additional patients has been planned for these situations).

A listing of patients excluded from the CP population will be provided with the reasons for their exclusion.

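### Protocol VII.2 takes a patient off study after a toxicity delay of more than 21 days, while VIII.2 and the schedule footnote require CT to continue until liver progression

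*Protocol*

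**What the plan says.** Protocol VII.2, in the paragraph on monitoring suspected everolimus toxicity, covers treatment that is "delayed for more than 21 days from the day of the next scheduled dose, the patient should be excluded from the study".

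Other parts of the current text treat the same patient differently:

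- **Protocol VIII.2** covers stopping for any reason other than hepatic progression and gives toxicity as its first example. It requires "CT every 3 months until liver progression occurs, according to the same modalities as the initial morphological evaluation".
- **Examination schedule, footnote \*\*\***: "If everolimus is discontinued for reasons other than hepatic progression, continue morphological monitoring until hepatic progression occurs".
- **Tables 1-1 and 1-2** have nearly the same trigger. For "Any non-hematologic toxicity requiring interruption for a period ≥ 3 weeks", and for the matching haematological row, the action is to stop everolimus. Neither table mentions study status.
- **Protocol XII.3**: "In all cases of discontinuation, the patient remains in the intention-to-treat analysis".

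Elsewhere the protocol keeps leaving the drug and leaving the study apart. For a hepatitis C flare (Table 2-3) it says "Discontinue study drug but continue monitoring as part of the study". For pregnancy (section XI) it says "if a pregnancy is discovered after inclusion, the patient must be excluded from the trial".

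SAP 6.1.2 (primary endpoint population) counts a patient as evaluable after "at least one dose of everolimus and at least one treatment-related imaging". A patient with no 24-month or later CT, who has not already died or progressed in the liver, goes to a medical review that decides between failure and non-evaluable.

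**The concern.** A patient off everolimus for toxicity for more than 21 days falls under both rules. One takes the patient off study; the other keeps the patient in the CT schedule. Nothing in the protocol ranks them.

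The primary endpoint is the proportion alive without liver progression at 24 months, read from CT. If a site takes VII.2 at its word, the CT can be lost in two ways:

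1. **Before the first evaluation CT at three months.** On a plain reading of SAP 6.1.2, a living patient with no on-treatment imaging is not evaluable and drops out of the primary population.
2. **Later, with no CT at 24 months or beyond.** The patient goes to case-by-case review. A ruling of failure costs power. A ruling of non-evaluable removes a patient for a reason linked to treatment.

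The intention-to-treat Kaplan-Meier analysis of liver progression does not recover the information. SAP 5.7.2.2 censors such a patient at the last CT, or at inclusion plus one day if there is none. With a single open-label arm, there is no comparison group in which selective loss of this kind would show.

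**Working it through.** **Inputs from the documents.** H0 rate 35%, H1 rate 50%, one-sided alpha 5%, power 80%, exact binomial, 68 patients, 5% allowance, 72 included (SAP 5.5). Success if at least 31 of 68 evaluable patients are alive without liver progression at 24 months (SAP 5.6.1). First evaluation CT three months after the first embolization (Protocol VIII.1).

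**Assumptions, not in the documents.** The number of affected patients, k, and the true 24-month success rate among them, p_e.

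**Step 1: the plan's own figures.**
- P(X ≥ 31 | n = 68, p = 0.35) = 0.046
- P(X ≥ 31 | n = 68, p = 0.50) = 0.802
- 68 / 0.95 = 71.6, rounded up to 72

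All agree with the plan.

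**Step 2: when the first route opens.** Three months is 3 × 30.4375 ≈ 91 days after the first embolization. An interruption that starts before about day 91 − 21 = 70 passes 21 days before that CT.

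**Step 3: affected patients ruled failures.** Keep 68 evaluable patients and force k of them to failure. The other 68 − k must supply all 31 successes, so power = P(X ≥ 31 | 68 − k, 0.50).

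| k | Power |
|---|---|
| 0 | 80.2% |
| 1 | 76.8% |
| 2 | 73.1% |

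This is a worst case. It assumes that none of the k would have been rightly counted as a failure anyway beyond the planned 50% rate in the rest, and that the four-patient allowance (72 − 68) is used up by other patients.

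**Step 4: affected patients ruled non-evaluable.** Let the true rate over all 72 be 35%. Remove k patients whose own rate is p_e. The rate among those left is

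q = (72 × 0.35 − k × p_e) / (72 − k).

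Any other removals, up to the allowance of four, are taken as unrelated to outcome, so 68 are analysed and the false-positive chance is P(X ≥ 31 | 68, q). For example, with k = 2 and p_e = 0, q = 25.2 / 70 = 0.360.

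| k | p_e = 20% | p_e = 10% | p_e = 0% |
|---|---|---|---|
| 1 | 5.0% | 5.2% | 5.5% |
| 2 | 5.4% | 6.0% | 6.6% |
| 4 | 6.3% | 7.7% | 9.3% |

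If p_e is 35%, the same as everyone else, the chance stays at 4.6% for any k. With 68 still analysed, power at a true rate of 50% in those patients stays at 80.2%.

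**The case against.** The strongest reply is that the protocol already points one way. Section VIII is the follow-up section, names toxicity and requires CT to continue. The footnote repeats this without exception, Tables 1-1 and 1-2 only stop the drug, and XII.3 keeps discontinued patients in the intention-to-treat analysis. A note in VIII.1 repeats the monitoring sentence of VII.2 almost unchanged and leaves out the exclusion. The text is visibly translated, so a slip between treatment and study is plausible. VII.2 does not say that imaging stops. Even in the pregnancy case, exclusion is followed by further follow-up, although for safety and not by CT.

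Much of this stands: stopping the drug is the likelier intention, and the loss of CT is an inference from the ordinary meaning of exclusion. It does not remove the conflict. An analysis rule such as XII.3 does not tell a site to keep scanning, and a site reading the dose-adjustment section finds an explicit instruction.

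A second reply is that the 5% allowance covers non-evaluable patients. It covers their number, but it does not correct for loss linked to outcome.

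A reader might go further and infer that the review's ruling on four such patients would decide the trial, by comparing 31 successes out of 68 with 31 out of 72. The documents do not support that. SAP 5.6.1 states its decision rule only for 68 evaluable patients, and the discretion between failure and non-evaluable belongs to SAP 6.1.2. It applies to any patient without a 24-month CT and would remain after VII.2 is corrected.

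**Conclusion.** The concern holds as an internal inconsistency that should be corrected: an explicit instruction in VII.2 conflicts with VIII.2, the schedule footnote and the dose tables. If followed literally, it could end primary-endpoint imaging for a treatment-related reason.

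The effect is probably modest. With one or two affected patients, power drops by about 3 or 7 percentage points if they are ruled failures. If they are removed instead, the false-positive chance moves from 4.6% to between 5.0% and 6.6%. The figure of 9.3% needs all four removals to be toxicity-linked and none of those patients to be a true success. These sizes depend on assumed values of k and p_e, and on a site setting aside VIII.2 and the footnote for a patient who has not already died or progressed in the liver.

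It should not be read as a fault in the sample size, alpha or power, all of which reproduce. Nor do the documents show that scanning would in fact stop at any site.

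**What to change.** In Protocol VII.2, replace the instruction to exclude the patient from the study with: *everolimus is permanently stopped and CT follow-up continues per VIII.2*. In the same sentence or next to it, state that hepatitis B reactivation remains under the 28-day rule of Table 2-2, so that the 21-day limit is not applied there.

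The cost is a one-sentence protocol clarification. Sample size, decision rule and analysis do not change. CTs that have been missed cannot be recovered, so sites need the correction while patients are still in follow-up.
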